***Exclusion Criteria***

- Neurologic conditions that affect bladder function, such as multiple sclerosis, spinal cord injury, Parkinson's disease, or other neurogenic bladder conditions.
- Significant pelvic organ prolapses or other pelvic pathology that interferes with bladder emptying, neuromodulation efficacy, or study assessments
- Active urinary tract infection (UTI) or unexplained hematuria at screening
- Clinically significant post-void residual (PVR) volume above threshold (e.g., >100 mL)
- History of, failure of, or current use of neuromodulation therapies, including percutaneous or transcutaneous tibial nerve stimulation (PTNS/TTNS), sacral neuromodulation (InterStim), implantable tibial devices (eCoin)
- Intravesical botulinum toxin injections less than 9 months prior to entry into the study
- Pregnancy or plans to become pregnant during study participation, and women of childbearing age not using contraception. A urine pregnancy test will be performed for women of childbearing potential to confirm non-pregnant status prior to enrollment.
- Contraindications to electrical stimulation (cardiac pacemaker or implanted defibrillator without physician clearance, unhealed wounds near stimulation site, metal implants in the ankle region)
- Significant uncontrolled medical conditions, such as unstable cardiac disease, poorly controlled diabetes mellitus, severe peripheral edema, or severe peripheral neuropathy that may affect lower-limb sensation or response to stimulation in the opinion of the investigator
- Pelvic malignancy of GI, GU or GYN origin, or prior pelvic radiotherapy.
- Current participation in another investigational drug or device trial, or use of an investigational therapy within the last 30 days
- Known hypersensitivity or intolerance to materials used in the ZIDA device (electrode adhesives, conductive gels)

**6.0 Number of Subjects**

20

**7.0 Setting**

The study will be conducted at MUSC's Department of Urology. Participants will administer their treatment at home.

**8.0 Recruitment Methods**

Potential participants will be identified through MUSC Urology clinic visits or by using Epic EHR review to locate adults with a diagnosis of OAB-wet who are on stable pharmacotherapy and may meet eligibility criteria. Prescreening will be performed by authorized study staff through chart review only; no direct patient contact will occur at this stage. When a potentially eligible patient is identified through chart review, the study team will notify the treating clinician prior to the patient's upcoming appointment. The treating clinician will briefly introduce the study during the clinical encounter. If the patient is interested in participating in this study, the clinician will ask for permission from the patient for the research team to follow up with them. Study staff will only

contact potential participants after permission has been confirmed. The research coordinator will be present in clinic to come speak with the patient.

Some eligible patients may be missed during prescreening. Their treating clinician (including attending physicians, fellows, and PAs within the MUSC Urology clinic) also have the option to identify eligible patients during clinic. In these cases, clinicians may briefly inform the patient about the study and, if the patient is interested, get permission for the research team to follow up. The research coordinator will be present in clinic to come speak with the patient.

Recruitment will occur on a rolling basis over approximately 10 to 14 months, with an estimated enrollment rate of 1.5 to 2 participants per month.

## **9.0 Consent Process**

Informed consent will be obtained from all participants before any study-related screening procedures are conducted. The consent process will take place in a private setting. Consent will be obtained by IRB-approved study personnel either in person during the participant's screening visit (which may coincide with a routine clinic appointment) or remotely via a secure HIPAA-compliant telehealth platform. Participants will be provided the consent form and given adequate time to review it and ask questions before signing. Individuals who wish to consider participation further will be offered at least 24 hours for reflection before providing consent. The study team will make sure that participants understand that their participation is voluntary and that their refusal or withdrawal at any time will not affect their clinical care. This consent form will explain that screening procedures to confirm final eligibility for enrollment will take place after consent. The participant will receive copy of their signed consent form.

## **10.0 Study Design / Methods**

After providing informed consent, participants will complete a 14-week study consisting of a screening visit, baseline visit, 12 weeks of home treatment, remote check-ins, and a final in-person visit.

### **Screening Visit:**

Participants may complete informed consent either remotely before the screening visit or in person at the time of screening, depending on preference. Once they have been consented, they will begin the screening visit, which may occur with a routine clinic appointment. At the screening visit a physical exam will occur. If a patient is already having the procedure or exam per standard of care for their clinic visit, we will not repeat the procedure but will instead review the medical record for the results. During this visit, the following will occur:

- medical history and medication review,
- physical examination,
- urinalysis (to assess for hematuria or UTI),
- urine dipstick pregnancy test for women of childbearing potential (the test will be done on the same urinalysis urine sample when possible),

- post-void residual (PRV) volume measurement. This will be conducted by using a non-invasive ultrasound scanner after voluntary voiding to assess for incomplete bladder emptying and rule out urinary retention.
- completion of baseline questionnaires, including the OAB-Q SF 1W and the PGI-S. The OAB-Q SF 1W is a validated 19-item questionnaire that is used to assess patient quality of life. The PGI-S is a single item scale that measures symptom severity. Study questionnaires may be completed on paper or electronically through REDCap, depending on participant preference.

After these screening procedures are done and eligibility is confirmed, the participants will be enrolled in the study. Study-related procedures will only be conducted by clinicians who are members of the study team.

**Baseline Visit (same day or on a different day):**

- Participants go over the screening results and confirm their enrollment in the study.
- Participants will be instructed that they should remain on stable OAB pharmacotherapy throughout the study.
- They will receive the ZIDA device and get device training based on the ZIDA manufacturer's IFU. They will be instructed to call the study team if, while using the device, they experience any pain, skin irritation, or technical problems.
- They will also be given a 3-day bladder diary and instructions on how to complete it at home over three consecutive days before starting device therapy. This diary records voiding time, urgency, and urgency-urinary-incontinence episodes.
- They will also receive the Device Use Logs, Adverse Event Logs, and Bladder Diaries for the entirety of the study.
- The baseline visit may occur on the same day as the screening visit or may be scheduled for a later date, depending on when all screening procedures are completed and eligibility is confirmed. If all screening assessments are finished during the initial clinic encounter and the participant has enough time to complete the baseline visit, then the baseline visit could be completed. Or, if preferred by the participant, the baseline visit may also be conducted remotely after the screening visit. If this is the case (once eligibility is confirmed) the participant will receive all of the required study materials; the ZIDA device, IFU, conductive gel, and all study logs (Device Use Log, Adverse Event Log, and bladder diaries). Then device training will be conducted either in person or remotely before the participant begins device use. Participants who do not have time to complete all screening and baseline activities in a single visit may return for one additional visit (combined Screening and Baseline visit) to finish any screening procedures and the baseline visit. In all scenarios, the participants will complete all screening procedures, then once they meet eligibility criteria, will receive device training, and receive all study materials before beginning the intervention period.

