### *Inclusion Criteria*

- Age  $\geq 18$  years
- Diagnosis of OAB-wet (OAB with urgency urinary incontinence) documented by clinical diagnosis
- Baseline  $\geq 1$  UUI episode/day averaged over a 3-day diary
- Is on a stable pharmacotherapy for OAB (antimuscarinic or  $\beta 3$ -agonist) for  $\geq 4$  weeks, with intent to remain on their medication regimen for the duration of this study
- Has the ability to complete bladder diaries, questionnaires, and attend follow-up visits
- Cognitively intact adult and able to understand study procedures and provide informed consent independently.
  - A study team member at the informed consent conversation will assess cognitive ability and the ability to provide informed consent. Assessment will be based on the participant's ability to understand the study procedures and accurately restate their study roles in their own words. No formal cognitive testing will be performed.

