## **11.0 Data Management**

All data will be limited to clinical and patient-reported outcomes (e.g., bladder diaries, questionnaires, adverse event logs). Collected data will include demographic information

(age, sex), OAB history, current medications, baseline and follow-up diary metrics, and questionnaire scores. Research data will be coded. Identifiable patient information will be stored in a linking document and stored separately from the research data in a password-protected software accessible only to authorized study staff. All study staff will complete CITI training in human subjects research and will be HIPAA compliant. Only de-identified patient data will be removed from MUSC servers. Hard copy documentation (like consent forms and bladder diaries) will be stored in locked cabinets within MUSC Urology research offices. Any data collected electronically (eg. Electronic consents or questionnaires) will be stored in REDCap. Paper responses will be entered into REDCap by study staff, and hard copies stored as source documentation. If any participants complete electronic consent via REDCap's e-consent module, those signed forms will be stored securely within REDCap under MUSC's encrypted server.

- For this single arm pre/post study design, we plan to enroll a total of 20 participants. Since we expect no more than 20% drop-out, this will yield complete data on at least 16 participants. A sample size of  $n=16$  provides 85% power to detect modest changes (effect sizes of 0.7) in study outcomes, including Total Daily Incontinence episodes). Earlier work by Cava & Orlin (2022) suggest that the device may yield an even larger decline in incontinence episodes (i.e. from  $1.2 \pm 0.8$  at baseline down to  $0.3 \pm 0.3$ , at week 12, corresponding to an effect size of 1.4), meaning that we may likely have even greater statistical power. This sample size would also provide sufficient power (>80%) to detect changes in secondary outcomes, including Quality of Life (OAB-Q SF 1W total score). While primary analysis compares baseline to week 12, repeated-measures models will incorporate interim timepoints (weeks 1, 4, 8) descriptively.

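### The 3-day diary that decides eligibility is first handed out after eligibility is confirmed and the patient enrolled, and no review is required before the first session

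*Protocol*

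**What the plan says.** Protocol section 5.0 (Inclusion Criteria) requires a baseline of at least one "UUI episode/day averaged over a 3-day diary".

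Section 9.0 sets the earliest point at which a study diary could be collected: "Informed consent will be obtained from all participants before any study-related screening procedures are conducted".

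Section 10.0, Screening Visit, lists history and medication review, physical examination, urinalysis, pregnancy test, post-void residual, OAB-Q SF 1W and PGI-S. No bladder diary is listed. The section ends: "After these screening procedures are done and eligibility is confirmed, the participants will be enrolled in the study".

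Section 10.0, Baseline Visit, then covers the device ("They will receive the ZIDA device and get device training based on the ZIDA manufacturer's IFU") and the diary: participants are "given a 3-day bladder diary and instructions on how to complete it at home over three consecutive days before starting device therapy". On timing, "The baseline visit may occur on the same day as the screening visit". For every scenario the order is that "the participants will complete all screening procedures, then once they meet eligibility criteria, will receive device training, and receive all study materials". The same paragraph counts the bladder diaries among those materials.

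Section 10.0, Intervention Period, puts the next scheduled contact at the Week 1 check-in, whose stated tasks are the Device Use Log and adverse events. Paper diaries may be read out at a telehealth check-in or collected at the final visit. The Final Visit text has participants hand in their diaries then.

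Section 11.0 plans 20 enrolled, at most 20% drop-out and at least 16 complete, and says that 16 "provides 85% power to detect modest changes (effect sizes of 0.7) in study outcomes".

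**The concern.** The rule is circular: the diary is needed to establish eligibility, and eligibility must be established before the diary is given out. A team following section 10.0 literally will declare patients eligible without the one measurement that defines severity at entry.

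This diary also supplies the baseline of the primary endpoint (section 4.0), and each patient is their own control (section 3.0). Two things are therefore at stake:

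- **Population.** Patients below one episode per day can be enrolled and treated, so the analysed group may not be the one section 5.0 defines. If they are removed instead, the loss falls on the 20, and section 11.0 makes no allowance for ineligibility found after enrolment.
- **Baseline.** If the diary is missing or unusable and this is noticed only after the first session, an untreated baseline for that patient can no longer be obtained.

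**Working it through.** **1. Order of events.**

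| Step | Event | Source | UUI/day known from a study diary? |
|---|---|---|---|
| 1 | Consent | 9.0 | No |
| 2 | Screening procedures, no diary | 10.0 Screening | No |
| 3 | Eligibility confirmed, patient enrolled | 10.0 Screening | No |
| 4 | Device, training and diary given | 10.0 Baseline | No |
| 5 | Diary kept at home for three days | 10.0 Baseline | Known to the patient; no staff review specified |
| 6 | First session | 10.0 Intervention | No review required beforehand |

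The criterion from section 5.0 is needed at step 3, and its data arise at step 5. When screening and baseline fall on one day, steps 2 to 4 happen together and no three-day interval exists before enrolment.

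**2. Readings that might remove the conflict.**

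- The Screening Visit lets staff use medical-record results for a procedure or exam already done as standard care. A diary is not on the screening list, and no routine clinic diary is mentioned.
- Section 12.0 allows withdrawal of patients who cease to meet the criteria. Its examples are stopping medication and non-adherence, so it is not a screen-failure rule for the baseline diary.

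Neither reading resolves the order.

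**3. The plan's own figures.** Enrolment: 16 / (1 − 0.20) = 20, which reproduces. Power for a paired t-test comes from the noncentral t distribution with n − 1 degrees of freedom and noncentrality d√n. At n = 16 and d = 0.7 the noncentrality is 0.7 × 4 = 2.8. The section states neither alpha nor sidedness. With alpha 0.05 assumed, power is 84.7% one-sided, which matches the stated 85%, and 74.5% two-sided.

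**4. Illustration of removal after enrolment.** Let f be the share of the 20 who fail the diary criterion and are removed. This is an assumption; the documents give no value. With 20% drop-out in the rest, completers = 20 × (1 − f) × 0.8. Enrolment needed to keep 16 = 16 / [0.8 × (1 − f)], rounded up.

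| f | Completers | Two-sided power, d = 0.7 | One-sided power, d = 0.7 | Enrolment needed for 16 |
|---|---|---|---|---|
| 0 | 16 | 74.5% | 84.7% | 20 |
| 10% | 14.4, about 14 | 67.8% | 79.8% | 23 |
| 20% | 12.8, about 13 | 64.0% | 76.8% | 25 |
| 30% | 11.2, about 11 | 55.4% | 69.7% | 29 |

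Like for like, 10% removal costs 74.5 − 67.8 = 6.7 points two-sided, or 84.7 − 79.8 = 4.9 points one-sided.

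**The case against.** The best defence is that the diary must be kept before device therapy starts, so the qualifying data exist before any stimulation. REDCap entry would let staff see them, and about 14 weeks of participation around 12 weeks of treatment leaves room for a check. This stands in part. A reader might infer that the criterion cannot be applied at all, or that the protocol directs treatment of patients below the threshold. The text supports neither: a timely check is possible, but it is not required, and enrolment has already happened by then.

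Three further inferences should be resisted.

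- **Setting 68% against the stated 85%.** Most of that gap is sidedness, a separate matter. The comparators are 74.5% two-sided and 84.7% one-sided at n = 16. If the effect size of 1.4 cited in section 11.0 held, two-sided power would still be 99.8% at n = 14 and 98.6% at n = 11.
- **Reading a failure rate off the earlier trial.** A normal curve with its baseline of 1.2 ± 0.8 puts Φ((1 − 1.2)/0.8) = Φ(−0.25) = 40% below one per day. But the documents do not show that medicated clinic patients with persistent UUI resemble that sample, and the result depends on the assumed distribution.
- **Claiming that low-frequency patients would dilute the effect.** They have less absolute room to improve. Yet the only data cited fell from 1.2 to 0.3, reported as an effect size of 1.4, despite a baseline mean near the threshold. The documents do not show a smaller standardised effect.

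**Conclusion.** The contradiction between section 5.0 and the Screening and Baseline Visit text of section 10.0 is real and depends on no assumed number. As written, eligibility is confirmed and enrolment completed without the diary the criterion needs, and no step secures that diary before the first session. With paper diaries, staff might not see it until the final visit, since nothing treats the baseline diary differently from the later ones.

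The numerical cost is uncertain because the failure rate is unknown. Under the assumed 10% to 30% removal, with 20% drop-out, alpha 0.05 and d = 0.7, completers fall from 16 to between 14 and 11. Two-sided power falls from 74.5% to between about 68% and 55%. If nobody failed the criterion, the sample size would be unaffected, but the check on the primary baseline would still be missing. This belongs in the protocol, since it concerns when patients are enrolled, and should be reconciled before recruitment.

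**What to change.** Amend the Screening and Baseline Visit text of section 10.0 so that:

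1. the 3-day diary is given after consent;
2. the study team reviews the completed diary, through REDCap or by phone, against the section 5.0 criterion;
3. eligibility is declared, the patient counted toward the 20, and device use begun only after that review.

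The sentence that fixes the order for all scenarios should be changed to match, so that the diary is no longer among the materials withheld until eligibility is met. Same-day visits need not end: the other procedures and the training can stay together, provided enrolment and the first session wait for the review.

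The cost is one short remote contact per patient and a few days' delay for some. Remote baseline visits, REDCap diaries and about two weeks beyond the 12 treatment weeks are already in the plan.

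One consequence should be acknowledged in the report. Selecting on the same diary that serves as baseline invites regression to the mean, which a single-arm pre-post comparison cannot separate from benefit. The existing criterion already implies this; enforcing it makes the point more visible.

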**Intervention Period (Weeks 1–12):**

- Participants will self-administer the ZIDA therapy once a week for 30 minutes. They choose a day of the week that works best for them. For each session, the participant will be seated comfortably, they will put conductive gel on the inside of the ZIDA sock, connect the control unit, and turn it on to begin electrical

stimulation. After 30 minutes, the device will automatically turn off. Participants take off the device, clean off any leftover gel. Participants will complete one session every week for 12 weeks (ideally on the same day  $\pm 24$  hours). Reminders may be sent by telephone, secure email, or text message through a HIPAA-compliant system, depending on participant preference. Reminder messages will be brief and only related to the study (e.g., “Please remember to do your session this week”).

- They will be asked to complete a Device Use Log after each session where they will write down the date, duration, and any notes about the session.
- Study staff will conduct remote study check ins at weeks 1, 4 and 8. Participants may choose to do these using a HIPAA-compliant telehealth platform or a phone call. During these check ins, the study team will confirm that patients are using and adhering to the session schedules by reviewing the Device Use Log. During remote visits, adherence will be confirmed either verbally by the participant reading their Device Use Log entries during the call, or through secure REDCap data entry if the participant prefers to complete their weekly log electronically. During these remote visits, the study team will record any adverse events or side effects. Adverse events and device-related complaints are documented on a standardized Adverse Event Log and reviewed by the study team and/or principal investigator. 3 Day Bladder Diaries: Participants will complete additional 3-day bladder diaries at Weeks 4, 8, and 12. Reminders may be sent by telephone, secure email, or text message through a HIPAA-compliant system, depending on participant preference. Reminder messages will only have neutral content that is relevant to the study (e.g., “Please remember to complete your bladder diary this week”). Participants may complete the 3-day bladder diaries on paper or electronically on REDCap given their preference. Paper diaries may instead be reviewed verbally during the telehealth check-in or collected at the final visit.

#### **Final Visit (Week 12) In person study visit:**

- Participants will return their bladder diaries
- Patients will again complete the OAB-Q SF 1W, PGI-S,
- Patients will complete a PGI-I, and Usability and Satisfaction Survey questionnaires. The PGI-I is a single item scale that measures symptom improvement.
- PVR measurement will be repeated using a bladder scanner
- All Device Use Logs will be collected and reviewed with the participant.
- Adverse events will be collected, and the Adverse Event Log will be reviewed with the participant.

The participant will return the device and any additional supplies they had received from the study team. Total participation is approximately 14 weeks.

## **11.0 Data Management**

All data will be limited to clinical and patient-reported outcomes (e.g., bladder diaries, questionnaires, adverse event logs). Collected data will include demographic information

(age, sex), OAB history, current medications, baseline and follow-up diary metrics, and questionnaire scores. Research data will be coded. Identifiable patient information will be stored in a linking document and stored separately from the research data in a password-protected software accessible only to authorized study staff. All study staff will complete CITI training in human subjects research and will be HIPAA compliant. Only de-identified patient data will be removed from MUSC servers. Hard copy documentation (like consent forms and bladder diaries) will be stored in locked cabinets within MUSC Urology research offices. Any data collected electronically (eg. Electronic consents or questionnaires) will be stored in REDCap. Paper responses will be entered into REDCap by study staff, and hard copies stored as source documentation. If any participants complete electronic consent via REDCap's e-consent module, those signed forms will be stored securely within REDCap under MUSC's encrypted server.

- For this single arm pre/post study design, we plan to enroll a total of 20 participants. Since we expect no more than 20% drop-out, this will yield complete data on at least 16 participants. A sample size of  $n=16$  provides 85% power to detect modest changes (effect sizes of 0.7) in study outcomes, including Total Daily Incontinence episodes). Earlier work by Cava & Orlin (2022) suggest that the device may yield an even larger decline in incontinence episodes (i.e. from  $1.2 \pm 0.8$  at baseline down to  $0.3 \pm 0.3$ , at week 12, corresponding to an effect size of 1.4), meaning that we may likely have even greater statistical power. This sample size would also provide sufficient power (>80%) to detect changes in secondary outcomes, including Quality of Life (OAB-Q SF 1W total score). While primary analysis compares baseline to week 12, repeated-measures models will incorporate interim timepoints (weeks 1, 4, 8) descriptively.
- Initially, descriptive statistics will be used to characterize the study participants at baseline and at follow-up. Continuous outcomes (i.e. measures of incontinence and quality of life) will be compared pre- and post-use of the device using paired t-tests, or Wilcoxon signed rank tests (if necessary). The proportion of participants who have no incontinence at follow-up will be reported, and these percentages will be compared using McNemar's tests for paired binomial proportions. The results of this study will be vital for helping to design a larger, definitive 2-arm randomized controlled trial.

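### The primary paired test in effect uses only participants with both diaries; a likelihood-based repeated-measures model as primary would lessen drop-out bias, with little gain in precision

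*Protocol*

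**What the plan says.** Section 11.0 (Data Management) of the protocol states that "we plan to enroll a total of 20 participants" and continues: "Since we expect no more than 20% drop-out, this will yield complete data on at least 16 participants". It says that this number "provides 85% power to detect modest changes (effect sizes of 0.7) in study outcomes". It then assigns the roles: the primary analysis sets Week 12 against baseline, while "repeated-measures models will incorporate interim timepoints (weeks 1, 4, 8) descriptively". The next paragraph says that continuous outcomes "will be compared pre- and post-use of the device using paired t-tests, or Wilcoxon signed rank tests (if necessary").

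Four other places bear on the point:

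- Sections 1.0 and 4.0 define the primary quantity as a mean change in daily episodes.
- Section 10.0 (Intervention Period) schedules post-baseline 3-day diaries at Weeks 4, 8 and 12. None is scheduled at Week 1. Paper diaries may be handed in only at the final visit.
- Section 12.0 lets the study withdraw participants who stop their medication, do not adhere to the device or have an adverse reaction. Data up to withdrawal are kept unless the participant asks for removal.
- Section 11.0 closes by saying that the results will help design a larger randomized trial.

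**The concern.** A paired test without imputation uses only people who have both a baseline and a Week 12 diary. Someone who completes the Week 4 and Week 8 diaries and then leaves adds nothing to the primary result, although the protocol by default keeps those diaries. The complete-pairs mean is unbiased only if leaving is unrelated to the change in episodes. Non-adherence, stopping medication and adverse reactions are reasons that could well go with a poor response. If they do, the error favours the device, and the inflated effect would pass into the planning of the randomized trial.

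A second, smaller matter is the Wilcoxon option. It has no stated trigger, so the primary test may be chosen after seeing the data, and a signed-rank test does not estimate the mean change that sections 1.0 and 4.0 name. The earlier result quoted in section 11.0 (0.3 ± 0.3 at Week 12) lies close to zero, where skewness is likely, so the option may well be used.

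**Working it through.** **Inputs from the protocol.** 20 enrolled, at most 20% drop-out, so 20 × 0.80 = 16 complete pairs; standardised effect 0.7; diaries at baseline and Weeks 4, 8 and 12.

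**Inputs assumed, because the protocol does not give them.** Alpha 0.05; correlation between diaries 0.3 to 0.8; timing and cause of drop-out, varied below. Unless noted, results are in units of the SD of the Week 12 change.

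**1. The plan's own figure.** Paired t-test, n = 16, d = 0.7: noncentrality 0.7 × √16 = 2.8 on 15 df. One-sided 5% (critical value 1.753) gives 84.7%, which matches the stated 85%. Two-sided 5% (2.131) gives 74.5%. The power statement therefore rests on 16 complete pairs and, by inference, on a one-sided 5% test. Sidedness is a separate matter.

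**2. Bias of the complete-pairs mean.** Suppose the 4 of 20 with the highest drop-out score leave, where score = change seen so far + independent noise of equal SD. The 16 lowest of 20 standard normal values average −0.333. The bias is then −0.333 × corr(score, Week 12 change).

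- Leaving driven by the recorded Week 4 or Week 8 change: under equal correlations, early and final change correlate 0.5. The noise multiplies this by 1/√2, giving 0.354. Bias = −0.333 × 0.354 = −0.118.
- Leaving driven by the unseen Week 12 change: correlation 1/√2 = 0.707. Bias = −0.333 × 0.707 = −0.235.

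**3. Simulation against the likelihood estimate.** 8,000 runs per scenario, true change −0.70, unstructured covariance estimated from the data, correlation 0.5 and 0.7:

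| Drop-out | Complete pairs: mean (SE) | Likelihood model: mean (SE) |
|---|---|---|
| At random | −0.70 (0.247–0.252) | −0.70 (0.244–0.247) |
| Driven by recorded diaries | −0.81 to −0.82 (0.244–0.249) | −0.70 (0.252–0.256) |
| Driven by unseen Week 12 value | −0.94 (0.237–0.241) | −0.86 to −0.91 (0.239–0.244) |

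The complete-pairs biases agree with step 2. In the second row the overstatement is 0.114/0.70 = 16% to 0.123/0.70 = 18%. Root mean squared error at correlation 0.5, leaving driven by Week 4: √(0.114² + 0.248²) = 0.273 for complete pairs against √(0.005² + 0.253²) = 0.253 for the model.

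Further runs with skewed as well as normal outcomes, and with some participants leaving before Week 4, gave a complete-pairs bias of about 0.08 to 0.15 and a model bias of about 0 to 0.03 when leaving depended on recorded diaries. The model had the lower root mean squared error in every scenario.

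**4. Precision.** With the covariance known and 4 leavers giving a baseline diary only, the variance of the change is (1 − ρ²)/16 + (1 − ρ)²/20, against 2(1 − ρ)/16 for 16 pairs. At ρ = 0.7: 0.0319 + 0.0045 = 0.0364 against 0.0375, an SE ratio of 0.985 and an effective n of 16.5. Over the assumed correlations and drop-out times, the SE falls by 1.5% to 6.5% (effective n 16.5 to 18.3). Once the covariance is estimated, the gain is about 0 to 4% with normal outcomes and can reverse, as the second row of the table shows.

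**5. Scale.** If the quoted effect size of 1.4 for a fall from 1.2 to 0.3 uses the SD of the change, that SD is 0.9/1.4 = 0.64. A bias of 0.1 to 0.15 SD is then 0.06 to 0.10 episodes per day.

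**The case against.** A paired comparison of baseline with Week 12 is a legitimate primary analysis, and it matches the endpoint. The protocol states no analysis set, and rules for missing data may sit in a SAP that is not shown. That stands, and the missing rule is not the point. The point is what the protocol does fix: a paired test sized on complete pairs, with the repeated-measures models set aside as descriptive.

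Four stronger readings are tempting, and the documents do not support them.

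- *The model would use the diaries of all 20.* Someone who leaves before Week 4 has a baseline diary only, paper diaries may come back only at a final visit that leavers may miss, and data may be removed on request.
- *It would recover the precision of 20 participants.* Step 4 shows that it would not.
- *The right model is already planned.* The text says only that the models are repeated-measures. It does not say mixed or likelihood-based, and a repeated-measures ANOVA that drops incomplete cases would fit the same words. It also lists Week 1, when no diary is scheduled.
- *Bias would disappear.* It does so only under missing at random. The stated withdrawal reasons need not be predictable from earlier diaries, and if leaving depends on the unseen outcome most of the bias stays: 0.16 to 0.21 of 0.24.

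It is also fair that an unstructured covariance over four visits has 4 × 5/2 = 10 parameters from 20 people, that the outcome is probably skewed, and that a covariance fallback is itself triggered by the data. Naming the fallback in advance limits that last problem but does not remove it.

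**Conclusion.** The point holds as a matter of bias, not of precision. The primary test in effect rests on complete pairs, and if poor responders leave it overstates benefit by about 0.1 to 0.15 SD of the change, given 4 leavers of 20, leaving driven by recorded diaries and correlations of 0.5 to 0.7. A likelihood-based model removes nearly all of this under missing at random and only part of it otherwise. The SE gain is about 0 to 4% and nil in some scenarios. If no diary is missing, the unstructured model gives the same Week 12 estimate as the paired analysis, so nothing is lost in the estimate then.

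A reader might infer that the paired test is invalid, or that the model would make the study's effect estimate trustworthy. Neither follows. The paired test is sound if leaving is unrelated to response, and no handling of missing diaries makes up for the lack of a control arm. The correlations and drop-out mechanisms are assumptions; the protocol gives none.

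**What to change.** In section 11.0, make the primary analysis a likelihood-based mixed model for daily urgency incontinence episodes:

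- Visits: baseline and Weeks 4, 8 and 12, with visit as a categorical factor. Leave out Week 1 unless a diary is added there.
- Covariance: unstructured, with Kenward-Roger degrees of freedom and one simpler structure named in advance in case the model does not converge.
- Participants: everyone with a baseline diary.
- Primary result: Week 12 minus baseline mean change with a two-sided 95% confidence interval. Weeks 4 and 8 stay descriptive.
- Sensitivity analyses: the paired t-test and the Wilcoxon test on complete pairs, both always reported, so that the test of the mean change is not chosen from the data.

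The benefit depends on having the interim diaries of those who leave. Section 10.0 already allows REDCap entry or review of paper diaries during the check-in call; the protocol should ask that Week 4 and Week 8 diaries be captured then, and not left to the final visit.

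The cost is mainly wording, with no new participants or visits. It does mean specifying a model that the protocol has not yet specified, accepting more model assumptions at n = 20, and possibly falling back on the simpler covariance.
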